Endocrine therapy is the major treatment of choice for HR+/HER2- MBC.¹⁷ In premenopausal women with HR+ BC, endocrine therapy with or without ovarian ablation (by surgery, chemotherapy or luteinizing hormone-releasing hormone (LHRH)) is the preferred option.¹⁸ In post-menopausal HR+/HER2- MBC (without extensive visceral involvement), anastrozole, letrozole and exemestane are the standard hormonal therapies along with selective estrogen receptor modulators like tamoxifen or selective estrogen receptor degraders like fulvestrant.³ These treatment options are associated with a time to progression (TTP) and prolongation of progression free survival (PFS) ranging from 5 to 15 months.¹⁸ These treatment options are supported by clinical practice guidelines published by the National Comprehensive Cancer Network (NCCN) and European Society for Medical Oncology (ESMO) as preferred first-line options in patients who are antiestrogen naïve or who had prior estrogen therapy within one year.¹⁹ For MBC with significant visceral burden or rapid progression of disease, chemotherapy is recommended.³ The response rates associated with these endocrine therapies as first-line agents are up to 40% with all initial responders eventually acquiring resistance over time.³ Moreover, single-agent treatment with an aromatase inhibitor or tamoxifen has shown limited clinical benefit as well as selective ER degrader fulvestrant has modest activity in this patient population.²⁰⁻²² Hence, clinically it's important to identify new targets to develop effective therapies to improve patients' outcomes. Some potential molecular targets that are altered in BC patients are cyclin-dependent kinase 4 and 6 (CDK4/6), phosphatidylinositol 3-kinase/mammalian target of rapamycin (PI3K/mTOR) pathway, and poly adenosine diphosphate ribose polymerase.¹⁶

PI3K/mTOR and CDK4/6 inhibitors can reduce the resistance to endocrine therapy. CDK4/6 inhibitors control the cyclin D– CDK–retinoblastoma (Rb) pathway and may have a synergistic activity when combined with hormonal therapy, as well as, reduce the resistance acquired to that class of treatment.¹⁶

Palbociclib (IBRANCE®) is one such oral targeted agent that selectively inhibits cyclin-dependent kinases (CDKs) - CDK4 and CDK6 resulting in cell cycle arrest. It is indicated for the treatment of HR+/HER2-MBC in combination with letrozole as initial endocrine-based therapy in post-menopausal women.²³

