The efficacy and safety of palbociclib was assessed in PALOMA-1 trial: a randomized Phase 2 study of palbociclib in combination with letrozole versus letrozole alone. The study showed that participants who were treated with Ibrance® plus letrozole had median PFS of 20.2 months as compared to those treated with letrozole alone who reported median PFS of 10.2 months ($p=0.0004$).²⁴ Following its success, the Food and Drug Administration (FDA) granted accelerated approval of palbociclib in combination with letrozole in February 2015 and became the first CDK4/6 inhibitor to be approved as a cancer therapy by the FDA.²⁵ The label was later expanded to include aromatase inhibitor in this indication based on the follow-up of PALOMA-2 trial which was a Phase III study for post-menopausal patients with metastatic HR+/HER- BC receiving letrozole in combination with palbociclib versus patients receiving letrozole and placebo. The study showed that participants treated with Ibrance® in combination with letrozole had a greater PFS compared with patients treated with letrozole plus placebo (24.8 months vs. 14.5 months; $p<0.001$, respectively).²⁶ A regular approval was granted to palbociclib in February 2016 for a second indication: treatment of HR+, HER2-MBC in combination with fulvestrant in women with disease progression following endocrine therapy. This was following the success of Phase III PALOMA-3 trial, that showed that Ibrance® in combination with fulvestrant prolonged PFS (median PFS of 9.5 months) compared with placebo with fulvestrant (median PFS of 4.6 months; $p<0.0001$) in women with metastatic HR+/HER2- BC that had relapsed or progressed during endocrine therapy.²⁶

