8.2.1. Inclusion Criteria

Patients must meet all of the following inclusion criteria to be eligible for inclusion in the study: Patients must meet all of the following inclusion criteria to be eligible for inclusion in the study:

1. Age ≥ 18 years or older with diagnosis of adenocarcinoma of the breast with evidence of metastatic/locally advanced disease not amenable to treatment with curative intent.
2. Documented HR+ (ER+ and/or PR+) tumor based on local standards.
3. Documented HER2- tumor based on local standards.

4. Will initiate treatment with palbociclib plus letrozole/aromatase inhibitor or palbociclib plus fulvestrant in line with the licensed indication(s), as first or second line therapy for metastatic/locally advanced BC at enrollment.
5. Patients who in the opinion of the investigator are willing and able to comply with regular clinic visits.
6. Evidence of a personally signed and dated informed consent document indicating that the patient (or a legally acceptable representative) has been informed of all pertinent aspects of the study.

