8.7. Data Analysis

Detailed methodology for summary and statistical analyses of data collected in this study will be documented in a statistical analysis plan (SAP), which will be dated, filed and maintained by the sponsor. The SAP may modify the plans outlined in the protocol; any major modifications of primary endpoint definitions or their analyses would be reflected in a protocol amendment.

This is a descriptive study, and as such, no statistical testing will be conducted. Analyses will be conducted using Statistical Analysis System (SAS) (version 9.3 or higher). Summary statistics for patient demographics, clinical characteristics, treatment patterns and QoL will be performed. Summary statistics for continuous variables will include number of observations, mean, standard deviation, median, 1st and 3rd quartiles, minimum, and maximum. Summary statistics for categorical data will include number of observations, counts and percentages. Kaplan-Meier analyses will be performed on time-to-event outcomes, eg, TTP, response and death.

Exploratory stratifications will be conducted (where adequate numbers of patients permit) to explore differences by eg, country, line of therapy, menopausal status, de novo versus recurrent disease, age (<55 years vs. ≥55 years), and combination therapy (ie, palbociclib plus letrozole/aromatase inhibitor vs. palbociclib plus fulvestrant). The data may also be evaluated and presented by other meaningful subgroups, as outlined in the SAP.

Should missing data occur, the data will be analyzed as they are recorded in the eCRFs, and no imputation of missing data will be performed. The amount of missing values for data elements will be reported.

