- *Combination therapy (ie, palbociclib plus letrozole/aromatase inhibitor, palbociclib plus fulvestrant).* The combination of therapies will be determined at the Palbociclib treatment initiation. Palbociclib plus letrozole/aromatase inhibitor group will be defined as patients receiving Palbociclib and either Anastrozole, Letrozole or Exemastane. Palbociclib plus fulvestrant group will be defined as patients receiving Palbociclib and Fulvestrant. Other endocrine therapies will not be considered in this definition. Descriptive summary tables for the subgroup analysis by combination therapy line for the specified study objectives will be created as shown in [Table Shells 3, 15, 23, 31, 39, 46, 55, 63](#).
- *Line of therapy (1st or 2nd).* Line of therapy will be determined at the Palbociclib treatment initiation and defined as whether Palbociclib has been used as the first or second line endocrine therapy for metastatic/locally advanced BC. Descriptive summary tables for the subgroup analysis by combination therapy line for the specified study objectives will be created as shown in [Table Shells 4, 16, 24, 32, 40, 48, 56, 64](#).

- *Country (Egypt, Jordan, Lebanon, UAE, Qatar, Morocco and KSA).* Descriptive summary tables for subgroup analysis by country for the specified study objectives will be created as shown in Table Shells 5, 17, 25, 33, 41, 49, 57, 65.
- *Menopausal status (premenopausal vs. postmenopausal).* Menopausal status will be assessed at the Palbociclib treatment initiation. Descriptive summary tables for the subgroup analysis by menopausal status for the specified study objectives will be created as shown in Table Shells 6, 18, 26, 34, 42, 50, 58, 66.
- *Metastatic status (de novo vs. recurrent disease)* The recurrence of the disease will be assessed at the Palbociclib treatment initiation. Descriptive summary tables for the subgroup analysis by disease recurrence for the specified study objectives will be created as shown in Table Shells 7, 19, 27, 35, 43, 51, 59, 67.

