7. LIST OF TABLE AND FIGURE SHELLS

Table 2. List of Table and Figure Shells

Objective	Number	Description
Primary objectives 1, 2, Secondary objective 1	Table Shell 1	Summary of patients enrollment per country and site
	Table Shell 2	Descriptive summary table of clinical outcomes of Palbociclib treatment.
	Table Shell 3	Descriptive summary table of clinical outcomes of Palbociclib treatment by combination of therapies.
	Table Shell 4	Descriptive summary table of clinical outcomes of Palbociclib treatment by line of endocrine therapy.
	Table Shell 5	Descriptive summary table of clinical outcomes of Palbociclib treatment by country.
	Table Shell 6	Descriptive summary table of clinical outcomes of Palbociclib treatment by menopausal status.
	Table Shell 7	Descriptive summary table of clinical outcomes of Palbociclib treatment by metastatic status.
	Table Shell 8	Descriptive summary table of clinical outcomes of Palbociclib treatment by metastatic site.
	Table Shell 9	Descriptive summary table of clinical outcomes of Palbociclib treatment by age group.
Secondary objective 2	Figure Shell 1	Kaplan Meier plot to describe progression free survival by type of combination therapy.
	Table Shell 10	Descriptive summary table of the demographic and initial clinical profiles of BC patients who have received Palbociclib treatment as first line therapy for metastatic/locally advanced BC.
	Table Shell 11	Descriptive summary table of the demographic and initial clinical profiles of BC patients who have received Palbociclib treatment as second line therapy for metastatic/locally advanced BC.
	Table Shell 12	Descriptive summary table of the clinical profiles of BC patients at the initiation of Palbociclib treatment as first line therapy for metastatic/locally advanced BC.
Secondary objective 3	Table Shell 13	Descriptive summary table of the clinical profiles of BC patients at the initiation of Palbociclib treatment as second line therapy for metastatic/locally advanced BC.
	Table Shell 14	Descriptive summary table of Palbociclib treatment characteristics.
	Table Shell 14	Descriptive summary table of Palbociclib treatment

PFIZER CONFIDENTIAL

Objective	Number	Description
Secondary objective 4		characteristics by combination of therapies.
	Table Shell 15	Descriptive summary table of Palbociclib treatment characteristics by line of endocrine therapy.
	Table Shell 16	Descriptive summary table of Palbociclib treatment characteristics by country.

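### Outcomes are shown by partner drug and by line of therapy only one way, so a difference in line mix can appear as a partner-drug difference

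*SAP*

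**What the plan says.** There is no control arm. Among the exploratory stratifications, Protocol 8.7 lists "combination therapy (ie, palbociclib plus letrozole/aromatase inhibitor vs. palbociclib plus fulvestrant". SAP 3.2 carries this forward and assigns patients by partner drug at initiation, without regard to line: "Palbociclib plus fulvestrant group will be defined as patients receiving Palbociclib and Fulvestrant. Other endocrine therapies will not be considered in this definition". Line is a second, separate variable, "defined as whether Palbociclib has been used as the first or second line endocrine therapy for metastatic/locally advanced BC". SAP 3.2 forms the subgroups for one stratification variable at a time. SAP 6.1 asks for the primary outcomes to be stratified at least by combination and by line.

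The outputs in Annex 2 follow that one-way structure:

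- **Progression-free proportions, survival and ORR:** Table Shell 3 by combination, Table Shell 4 by line.
- **TTR, TTP and PFS:** Table Shell 55 by combination, Table Shell 56 by line.
- **Kaplan-Meier figures:** by combination only. One entry in SAP Section 7 reads "Kaplan Meier plot to describe progression free survival by type of combination therapy". SAP 6.3 allows plots by other categories if data permit.
- **Partner mix by line:** Table Shell 16 in Annex 2 counts each accompanying endocrine drug under first and second line. It shows no outcomes.

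Protocol 6.1 describes the two combinations at different points in treatment: "in combination with letrozole as initial endocrine-based therapy in post-menopausal women" (later widened to aromatase inhibitors), and "in combination with fulvestrant in women with disease progression following endocrine therapy". Inclusion criterion 4 accepts either combination "in line with the licensed indication(s), as first or second line therapy for metastatic/locally advanced BC at enrollment".

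**The concern.** By the protocol's own account, the fulvestrant group should contain more patients who have already progressed on endocrine therapy. Progression-free time is expected to be shorter in such patients whichever partner drug they receive. Pooled over line, the two columns of Shells 3 and 55 and the two Kaplan-Meier curves then mix any partner-drug difference with the difference in line. The separate tables by line do not resolve this, because they pool over partner drug.

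This is the only contrast between treatments in the plan, the only one named for the figures, and Protocol 11 foresees publication. Side-by-side proportions and curves invite comparison even when no test is attached.

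**Working it through.** The documents state no figure for this contrast, so there is nothing to reproduce. The only sample-size calculation (15 per country × 7 = 105, Protocol 8.5) concerns something else. What follows is an illustration of size.

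**Inputs from Protocol 6.1**
- Median PFS with letrozole as initial therapy: 24.8 months.
- Median PFS with fulvestrant after endocrine therapy: 9.5 months.
- Palbociclib plus letrozole in a US record-based study: 39.5% first line, 15.7% second line. Among first- and second-line users that is 39.5 / (39.5 + 15.7) = 71.6% first line, used here for the aromatase-inhibitor group.

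**Assumptions**
- Exponential times, S(t) = 0.5^(t/median).
- No partner-drug effect within a line.
- The whole 24.8 versus 9.5 contrast is due to line. This is an upper bound, because the two trials also differ in partner drug and population.
- First-line share in the fulvestrant group, f: not in the documents, so varied.

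**Within-line values**
- 12 months: 0.5^(12/24.8) = 71.5% and 0.5^(12/9.5) = 41.7%.
- 18 months: 60.5% and 26.9%.

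**Apparent gap** = (0.716 − f) × (first-line value − second-line value), from unrounded values:

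| f | 12 months | 18 months |
|---|---|---|
| 0% | 21.4 points | 24.0 points |
| 20% | 15.4 | 17.3 |
| 40% | 9.4 | 10.6 |
| 60% | 3.5 | 3.9 |
| 71.6% | 0 | 0 |

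**Sensitivity at 12 months**
- With an assumed second-line median of 14.5 months, the gap runs from 10.9 points (f = 0%) to 0.
- With an assumed 90% first line in the aromatase-inhibitor group and the 9.5-month median, it is 26.9 points at f = 0% and 20.9 at f = 20%.

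**Real-world figures by partner drug in Protocol 6.1**
- US, 12-month progression-free: 84.1 − 79.8 = 4.3 points.
- Argentina, 6-month PFS: 94 − 95 = −1 point.

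**Cell sizes if the two variables are crossed.** Take 200 patients (Protocol 8.1 and Table 3), with 20–50% on fulvestrant and 20–40% of those first line (both assumed).
- 20% on fulvestrant, 20% of them first line: 115, 45, 8 and 32 patients (aromatase inhibitor first and second line, then fulvestrant first and second line).
- 40% on fulvestrant, 40% of them first line: 86, 34, 32 and 48.
- Over the whole range the smallest cell has 8 to 32 patients. Near 50%, the 95% half-width 1.96 × √(0.25/n) is 34.6 points at n = 8 and 17.3 at n = 32, before any loss to censoring.

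**The case against.** The strongest case on the other side has four parts.

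- **No partner-drug question is posed.** No objective compares partner drugs. The stated purpose of exploring differences covers every stratifier alike, the strata are conditional on adequate numbers, and no testing is planned. This stands. A reader might infer that the plan sets out to compare the two partners and fails to do so; the documents do not support that. The weakness lies in how descriptive columns can be read.
- **The two variables are not kept wholly apart.** A reader might infer that no output crosses partner drug and line. Shell 16 does, and the first-line share of each partner drug can largely be worked out from it. Shell 15 (prior chemotherapy) and the shell on prior advanced-disease therapies by combination add to this. The gap is confined to outcomes.
- **The size may be small.** The cited real-world progression-free gaps by partner drug are far below 21 points. This stands as a warning against the top of the range. It does not show that line mix is harmless, because the protocol does not give the line mix behind those figures.
- **Line may not be the whole confounder.** The 9.5-month median comes from women who relapsed or progressed during endocrine therapy, whereas SAP 3.2 counts only endocrine lines for metastatic or locally advanced disease. A patient relapsing on adjuvant endocrine therapy can therefore be first line and still resistant. SAP 3.2 makes endocrine sensitivity only an optional stratifier. This stands, and it limits what crossing by line can achieve.

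**Conclusion.** The point holds as a cheap improvement to the outputs; it is not an analysis error. No outcome is reported within partner-by-line cells, and the protocol itself gives reason to expect the two groups to differ in line, so the pooled contrast can carry a line difference.

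Under no partner effect, with 71.6% of the aromatase-inhibitor group first line, the apparent 12-month gap lies between 0 and about 21 points. The upper end needs the whole difference between the two trial medians to be due to line and no first-line patients on fulvestrant. A reader might infer that a gap of about 21 points is to be expected. The documents do not support that: the fulvestrant line mix is unknown, the line effect used is an upper bound, and the range includes zero.

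**What to change.** In SAP 3.2 and 6.1, with the matching shells:

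1. Keep the pooled columns of Shells 3 and 55 as description.
2. Add the same outcomes, and the Kaplan-Meier curves, by combination within line of therapy wherever a cell reaches a minimum number of patients fixed in the SAP beforehand.
3. Print the first-line share under each pooled combination column.
4. State that the pooled columns are not a comparison of partner drugs, and that endocrine resistance may still confound within a line.

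Both variables are already recorded at palbociclib initiation, so the cost is SAP wording and a few extra tables and plots. The downside is sparse cells at about 200 patients: the smallest may hold roughly 8 to 32 under the assumed splits, with wide intervals, and some may fall below the minimum. Items 3 and 4 can be done however small the cells turn out to be.

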4. ENDPOINTS AND COVARIATES

Descriptive summary tabulations will describe the clinical outcomes of Palbociclib treatment, demographic and clinical characteristics of the patients as well as the treatment patterns in the study population. The patients' clinical profiles will be described at the time of BC diagnosis. The patients' demographics, clinical profiles of BC and characteristics of Palbociclib treatment will be described at the time of the Palbociclib treatment initiation. The adjuvant and supportive therapies as well as the Palbociclib treatments received by the study population during the observational period will be described.

4.1. Primary Endpoints

This study focuses on the patients who have received Palbociclib treatment for BC. The primary endpoints that describe the primary objectives in the study population will be:

- The clinical outcomes of Palbociclib treatment patients (proportion of patients that are progression free and alive after certain time intervals post palbociclib combination initiation)

4.2. Secondary Endpoints

The secondary endpoints that describe the secondary objectives in the study population and in the subgroups will be:

- Objective response rate (ORR);
- The clinical characteristics (*Time from initial breast cancer diagnosis to recurrence, staging, node status, menopause status, diagnosis for which palbociclib combination was prescribed, sites of metastases, de novo vs. recurrent disease*) of the study population;
- The demographics (*age, ethnicity, weight, family history of BC (BRCA; Testing performed*)) of the study population;
- Palbociclib treatment characteristics (schedule, dose, accompanying treatments, interruption, delays, discontinuation, duration);
- Supportive therapies received during palbociclib combination treatment;
- Adjuvant therapies (name, dose, frequency, initiation time, duration of the adjuvant therapies, and reasons for adjuvant therapy interruption, initiation, and failure) received for the treatment of early/locally advanced BC;
- Treatments received (treatment type, duration, and reasons for treatment changes) in the advanced/metastatic BC setting before and after Palbociclib treatment; Quality of life (QoL) of the patients during Palbociclib treatment.

4.3. Exploratory Endpoints

The exploratory endpoints that describe the exploratory objectives in the study population and in the subgroups will be:

- The clinical outcomes of Palbociclib treatment patients (time to response, time to progression and progression free survival);
- The first immediate subsequent treatment used following end of treatment with palbociclib.

4.4. Covariate and Variable Definitions

Patient demographics, clinical characteristics, comorbid conditions and concomitant medications, early/locally advanced and metastatic BC treatment history, current BC treatment, performance status (ECOG), clinical outcomes, laboratory investigations and QoL will be collected. Detailed definitions of the Data Entry Schedule and variables and are provided in Table 1 and Table 3 (Annex 1).

The definitions of clinical outcomes are presented in [Section 6.1](#), [Section 6.2](#), and [Section 6.3](#).

Table 1. Data Entry Schedule

Data collection and entry¹	Baseline	During treatment with Palbociclib	Post treatment with Palbociclib
	SOC Visit 1	SOC Follow-up visits² through End of Treatment with Palbociclib	SOC Follow-up visits through End of Study³
Informed Consent & Inclusion/Exclusion criteria	x		
Patient Demographics, Medical History, Baseline Metastatic Disease Status	x		
BC Diagnosis and Recurrence History	x		
Comorbid Conditions	x	x	
Concomitant Medications	x	x	
BC Treatment⁴	x	x	x⁵
Performance Status (ECOG)	x	x	
Clinical Outcomes⁶	x	x	
Laboratory Investigations, including CBC⁷	x	x	
EORTC QLQ-C30⁸	x	x	

BC=Breast cancer; SOC=Standard of care; CBC=complete blood count; ECOG=Eastern Cooperative Oncology Group; EORTC QLQ-C30=European Organization for the Reasearch and Treatment of Cancer Quality of Life Questionnaire C30.

1. Data is collected in accordance with normal standard of care visits; enter all data available per Data Entry Schedule into the electronic data capture system.
2. For all visits to be considered a follow-up visit, clinical outcomes data must be collected at minimum, in accordance with SOC.
3. Follow-up through End of Study; Enter data at SOC visits post palbociclib treatment.
4. BC treatment: including surgery, radiation, systemic chemotherapy, hormone therapy, and/or targeted therapy, in both neoadjuvant/adjuvant and metastatic disease settings, prior to, during and after palbociclib treatment; supportive care is also collected in the metastatic setting.
5. Data on the first immediate subsequent treatment used after the end of palbociclib treatment should be collected.
6. Clinical outcomes: overall clinical response as judged by treating physician, at intervals per standard of care schedule: progression free survival/time to progression, objective response rate, time to response and overall survival.
7. CBC: Baseline and during palbociclib treatment, enter any CBC during the 1st 3 cycles, then enter Day 1 (or prior to start of new cycle) CBC for the subsequent cycles as per standard of care.
8. EORTC QLQ-C30 will be collected at baseline (before starting palbociclib) then every 3 months \pm weeks after initiating treatment with palbociclib for the first year of treatment. After the first year of treatment with palbociclib, EORTC QLQ-C30 will be collected every 6 months \pm 4 weeks until the end of treatment with palbociclib.

PFIZER CONFIDENTIAL

CT24-WI-GL03-RF02 2.0 Non-Interventional Statistical Analysis Plan For Primary Data Collection Study 01-Jun-2020

Page 15 of 172

